Participants will be randomized to one of four messaging interventions; 1) active control (CDC TIPS from former smokers campaign), 2) active control (American Lung Association campaign), 3) treatment condition including message package focused on the link between smoking and dementia, 4) no intervention control. The messaging intervention will be delivered via mail, which will include a QR code link that will allow participants to view associated motivational video. Participants will then complete the first of 2 telephone survey assessments (lasting ~30 minutes). Participants will then receive three mailers over the next couple of months and will schedule their follow-up call approximately 2.5 months later. At one to two weeks, one month, and two months after this call they will be mailed the corresponding message to their group (no intervention group will not be sent a message package). Follow up telephone assessments will occur within approximately 1-2 weeks following intervention exposure marked by date the intervention mailer was sent.

Up to 20 participants randomized to the intervention condition will complete an additional brief qualitative interview following their second telephone survey assessment (lasting ~20 minutes). The qualitative interview will focus on the perceived impact of the message, preferred number of message exposures, preferred modality of message receipt, and suggested improvement to message content. Health Believe Model (HBM) constructs assessed include: perceived severity, perceived benefits (i.e., efficacy of EBSTs; impact of quitting on ADRD risk), perceived barriers (i.e., knowledge of how to access EBSTs in healthcare setting), and self-efficacy (i.e., confidence in ability to quit in the next 30 days).

4.

Incidental or Adventitious Findings

* Will any study procedures produce incidental or adventitious findings (e.g., imaging scans, laboratory blood tests, depression screening questionnaires, etc.)?

Yes **No**

5. Instruments/Technology Involved (Includes AI/ML Algorithms)

This question is intended to identify projects involving the development or use of medical devices. This does not apply to surveys, questionnaires, or statistical analysis software.

* Are there instruments or technology of any kind, including software, tests run on samples, and algorithms, used or developed in the study?

Yes **No**

Subject Identification: Medical Records

1. Medical Record Use

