The response to this question should address how the risk of breach of confidentiality will be minimized. For example, it could be described that the study team has several measures in place to protect against a breach of confidentiality, such as limiting the number of people who view identifiable information, coding study instruments, storing study data in restricted areas and on computers that are password-protected, only transmitting coded data outside the institution (if data will be shared), and using a secure web-interface to transmit data off-site (if data will be shared).

* Describe the procedures in place to minimize risks from all interventions performed for research purposes. This should include activities in place to identify, monitor, mitigate, and eliminate risks to the degree possible.

Data will be stored securely according to campus policy.

Participants will be informed of the approximate length of study activities during the consent process and will be offered the opportunity to take breaks during the study activities if needed.

Participants will be informed about all aspects of the study during consent and have the option to skip or withdraw from any activities that make them upset or uncomfortable.

Subject Population

1. Total Subjects

You must provide an integer. If you are enrolling a range of subjects (e.g., 50 to 100 subjects), enter the larger number.

* Provide the number of subjects that will be enrolled at sites for which UW Madison is serving as the reviewing IRB.

220

2. Inclusion Criteria

* Describe the main inclusion criteria.

- Adults between the ages of 50-80
- Self-reported current smoker
- Do not hold a current diagnosis of dementia or Mild Cognitive Impairment (MCI)
- Can read/write in English

3. Exclusion Criteria

* Describe the main exclusion criteria.

History of Mild Cognitive Impairment (MCI) or dementia.

4. Targeted Populations

Populations could be racial/ethnic, sex, or gender (this also applies to gender identity, or lack thereof).

* Will this study target or exclude specific populations?

Yes No

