1.3. No Consent/Assent

* Are there some participants from whom you will not obtain consent or assent?

Yes **No**

Waiver of Signed Consent

1. Waiver of Signed Consent Process

* Are you requesting a waiver of signed consent for all components of the study?

Yes No

2. Criteria

* Under which of the following criteria does this research qualify for waiver of signed consent? The research presents no more than minimal risk of harm to subjects and involves no procedures for which written consent is normally required outside of the research context.

3. Criteria Justification

* Provide a justification for the criterion selected above.

The research is a benign behavioral intervention that will be of minimal risk to the participants. Data security measures minimize the risk of breach of confidentiality, and the study activities do not normally require written consent outside the research context.

Consent Overview

1. Consent Process

* Describe the consent process, including when and where it will occur and how the consent process will be conducted (e.g., face to face, phone or video discussion) and how consent information will be provided to participants (e.g., in person, mailed/mailed).

Consenting will be done over the phone. After completing the Phone Screen, study staff will use the Study Information Sheet (see uploaded Study Information Sheet) to discuss study procedures and all elements of informed consent including:

- Study sponsor
- Invitation/Summary
- Study purpose
- Study participation, including assessments, schedule of study contacts, and treatment overview
- Risks, Benefits, and Costs
- Payment for participation
- How to revoke authorization
- Confidentiality
- How to contact study staff

We will provide a text copy of the the information sheet to the participants by mail after the initial call. Due to the screening and initial survey assessment occurring in the same call it is not feasible to provide the information to the participants prior to the first call. We will offer to email participants the information sheet if they explicitly ask for it, otherwise it will be mailed to participants.

2. Special Populations Involved

* Will the study enroll participants with limited English proficiency, who are illiterate/low-literacy, or have visual/hearing impairments?

Yes No

3. Qualification Affirmation

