4.1. Transcriber Details

* Indicate who will perform the transcription.

Transcription will be done by a professional transcription service.

Interviews, Focus Groups, Surveys, Questionnaires

1. Tool Details

* Describe the interview tools, questionnaires, or surveys that will be used. Click the add button to provide information about each tool to be used.

View	Tool Description	Optional Qualitative Interview
	Tool Standardized	No
	File name	Outline of Qualitative Interviews_V1_2023.10.13.docx
	Tool Manner	Telephone
	Tool Manner Other	No Value Entered
	Date Modified	10/20/2023

View	Tool Description	Follow Up Survey
	Tool Standardized	No
	File name	MCAS Aim 3 3 Month Follow Up Questionnaire_V2_10_20_23_trackedchanges.docx
	Tool Manner	Telephone
	Tool Manner Other	No Value Entered
	Date Modified	10/20/2023

View	Tool Description	Baseline Survey
	Tool Standardized	No
	File name	MCAS Aim 3 Baseline Questionnaire_V5
	Tool Manner	Telephone

Tool Manner Other	No Value Entered
Date Modified	9/13/2023

2. Cognitive or Psychological Assessment

* Are any of the uploaded instruments used to assess cognitive or psychological status or function?

Yes **No**

Interviews, Focus Groups, Surveys, Questionnaires Cont.

1. Focus Group

* Will the study involve conducting focus groups?

Yes **No**

2. In-Home Visit

* Does the study involve in-home visits?

Yes **No**

Supplemental Information

1. Additional Documents

Provide any additional relevant documents (e.g., data sharing agreements, letters of support, MOUs, site permission letters), if applicable.

-  active control flyer 1(0.01)
-  active control flyer 2(0.01)
-  active control flyer 3(0.01)
-  active control videos(0.01)
-  fear flyer(0.01)
-  fear video(0.01)
-  MCAS Mailing 1 Cover Letter Active Control and Treatment Condition (Groups 1, 2, 4)_v2(0.02)
-  MCAS Mailing 1 Cover Letter No Treatment Condition (Group 3)_v2(0.02)
-  MCAS Mailing 2 Cover Letter Active Control and Treatment Condition (Groups 1, 2, 4)_v2(0.02)
-  MCAS Mailing 3 Cover Letter Active Control and Treatment Condition (Groups 1, 2, 4)_v2(0.02)
-  MCAS Mailing for Follow-up Payment v1_11_8_23.docx(0.01)
-  MCAS Video Group 1 Email 1.docx(0.01)
-  MCAS Video Group 1 Email 2.docx(0.01)
-  MCAS Video Group 1 Email 3.docx(0.01)
-  MCAS Video Group 1 Email 3_V2_10_20_23_trackedchanges.docx(0.01)
-  MCAS Video Group 2 Email 1.docx(0.01)
-  MCAS Video Group 2 Email 2.docx(0.01)
-  MCAS Video Group 2 Email 3.docx(0.01)

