1.1. Describe Documents

Describe what additional documents were added in 1.

We have added a cover letter to be included with the participants' final study payment.

Final Page

1. Assurance

- The information presented in this application is accurate;
- If the application is being submitted on behalf of the Principal Investigator (PI) rather than by the PI, the information presented was done so with the PI's agreement; and
- The specific aims and description of research (including subject population, subject interventions, collaborators, performance sites, and general scope of work) in this IRB application are consistent with those described in the sources of support listed as providing financial and/or material resources to conduct this study.

* Do you certify the above statements?

Yes No

2. Complete and Submit Application Instructions

To complete and submit this application to the IRB office, please follow the steps below:

- Select 'Finish' or 'Exit' on this page to be directed to the application workspace.
- In the application workspace, click the Submit activity to send the application to the IRB office. NOTE: The Submit activity is only available to certain study team members.

Statistical Analysis Plan

[name] will use SPSS to examine differences in changes in motivation (primary), number of 24 hour quit attempts (secondary), and use of evidence-based treatment (secondary) between groups. Specifically, she will examine differences in mean scores from baseline and follow up between the treatment group and three control groups. Given the pilot nature of this study, we will not be statistically powered to conduct regression analyses. Therefore, descriptive analyses will be the primary analytic method.

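### Low power is a fair reason to make no confirmatory claim, but not a reason to leave baseline motivation out as a covariate (minor, nearly free improvement)

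*Combined protocol and SAP*

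**What the plan says.** The Statistical Analysis Plan, at the end of the combined document, is four sentences long. The analyst will "examine differences in changes in motivation (primary), number of 24 hour quit attempts (secondary), and use of evidence-based treatment (secondary) between groups". The contrast is then specified: "she will examine differences in mean scores from baseline and follow up between the treatment group and three control groups". The third sentence gives the reason for going no further, "Given the pilot nature of this study, we will not be statistically powered to conduct regression analyses", and the fourth concludes that "descriptive analyses will be the primary analytic method". No covariate, confidence interval or standard error is named there or elsewhere in the document.

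Three other places bear on the point.
- **Design.** Study Procedures and Interventions says "Participants will be randomized to one of four messaging interventions". It gives no allocation ratio.
- **Size.** Total Subjects under Subject Population gives 220, but the form's instruction reads "If you are enrolling a range of subjects (e.g., 50 to 100 subjects), enter the larger number", so 220 may be a ceiling.
- **Baseline data.** The tool list under Interviews, Focus Groups, Surveys, Questionnaires includes the file "MCAS Aim 3 Baseline Questionnaire_V5". The consent process under Consent Overview explains its timing with the words "Due to the screening and initial survey assessment occurring in the same call".

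**The concern.** The plan moves from low power to no regression. For hypothesis testing that is reasonable: a pilot should not claim a confirmatory result. For estimation it points the wrong way. Analysis of covariance is a linear regression whose usual purpose in a randomised trial is to remove outcome variation that baseline already explains. A small trial has more use for that than a large one, and here it needs no further participants or data.

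What is at stake is the precision of the primary estimate. With complete follow-up, the change score, the follow-up mean and the adjusted mean all estimate the randomised difference without bias. The secondary matter is that a pilot's between-arm difference is informative mainly through its interval, and the plan does not commit to giving one.

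**Working it through.** **Inputs.** From the documents: four arms, up to 220 participants, motivation measured at baseline and follow-up. Not stated, so assumed: equal allocation (220 / 4 = 55 per arm), the correlation r between baseline and follow-up motivation (0.3 to 0.7), equal SDs, no dropout, and the same baseline slope in every arm. The plan gives no power, SD or effect size, so there is no figure of its own to reproduce.

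**Formula.** In units of the follow-up SD, the 95% half-width for one contrast is 1.96 × s × √(2/n). At n = 55, 1.96 × √(2/55) = 0.374. With k = baseline SD / follow-up SD:
- change score: s² = 1 + k² − 2rk, which is 2(1 − r) when k = 1
- follow-up means only: s² = 1
- adjusted for baseline: s² = 1 − r²

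| r | Change score | Follow-up only | Adjusted |
|---|---|---|---|
| 0.3 | 0.374 × √1.40 = 0.442 | 0.374 | 0.374 × √0.91 = 0.357 |
| 0.5 | 0.374 × √1.00 = 0.374 | 0.374 | 0.374 × √0.75 = 0.324 |
| 0.7 | 0.374 × √0.60 = 0.290 | 0.374 | 0.374 × √0.51 = 0.267 |

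Against the change score, the interval narrows by about 19%, 13% and 8%. With 20% loss (44 per arm), the change-score and adjusted values are 0.494 and 0.399, 0.418 and 0.362, and 0.324 and 0.298.

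**Cost of the covariate.** One degree of freedom. For a two-arm comparison at 55 per arm, the t critical value moves from 1.9822 to 1.9824.

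**When the gain vanishes.** With a common slope, change-score variance minus adjusted variance is (1 + k² − 2rk) − (1 − r²) = (k − r)². It is near zero when k is close to r. At r = 0.7 and k = 0.8, s² for the change score is 1 + 0.64 − 1.12 = 0.52, giving 0.270 against 0.267.

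**When the gain reverses.** One model with a single slope pools that slope over all four arms. Suppose the slopes are 0.9 in treatment and one control and 0.1 in the other two arms, with k = 1. The pooled slope is 0.5. In the two compared arms the adjusted variance is 1 + 0.25 − 2(0.5)(0.9) = 0.35, a half-width of 1.96 × √(2 × 0.35/55) = 0.221. The change score has variance 0.20, a half-width of 0.167. Simulation agrees (about 0.22 against 0.17). Arm-specific slopes would restore the advantage: variance 1 − 0.81 = 0.19, half-width 0.163. In a milder case, with slopes 0.2, 0.6, 0.6 and 0.6, simulation still favoured the single-slope adjustment: 0.342, against 0.369 for follow-up only and 0.409 for the change score.

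**What an interval adds.** At r = 0.5, an observed difference of 0.3 SD would have a 95% CI of 0.30 ± 0.374 = −0.07 to 0.67 (change score) or 0.30 ± 0.324 = −0.02 to 0.62 (adjusted). For treatment use, if both arms are at 10%, 20% or 30%, the half-width 1.96 × √(2p(1 − p)/55) is 11, 15 or 17 percentage points.

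**The case against.** The plan does not mention analysis of covariance. Read naturally, its sentence about regression declines inferential modelling in a pilot, which is sensible. It already uses baseline by looking at changes in motivation, so the issue is a choice between two valid estimators. A reader might infer that the plan states low power as its reason for ignoring baseline. It does not: the exclusion of a covariate is inferred from the unqualified word regression. This part of the objection stands and keeps the point minor.

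A reader might also infer that adjustment can never lose precision. That holds only with a common baseline slope (and apart from the one degree of freedom). The unequal-slope case above shows a reversal, although it takes extreme slopes to produce one.

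Nor does the missing interval make the plan wrong. Descriptive analysis does not exclude intervals, and the document does not say that differences will be reported without them. By itself that is mostly missing detail.

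Finally, the covariate must be measured before any message. Study Procedures and Interventions first describes mail delivery and then the first survey, but later places the mailings after that call. The Consent Overview puts the first survey in the screening call. The later sentence and the consent text favour survey first, but the order is not settled. A change score would need the same clarification.

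**Conclusion.** The point holds as a minor improvement. Low power supports making no confirmatory claim. It does not support leaving baseline motivation out of the model for the primary outcome, provided regression is taken to cover analysis of covariance.

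The likely benefit over a change score is an interval 8% to 19% narrower for r between 0.7 and 0.3, assuming 55 per arm, equal SDs, no dropout and a common slope. The true gain for this trial is unknown, because r, the SDs, the allocation, the dropout and the motivation scale are not given in the text reviewed. It could be close to zero and, with strongly unequal slopes, negative. A reader might infer that the planned comparison is biased or that the study is undermined; with complete follow-up only precision is affected, and the documents give no dropout figures to support more than that.

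**What to change.** Confine the power remark to confirmatory hypothesis testing, and add text along these lines:

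*The primary estimate is the treatment-minus-control difference in follow-up motivation, from a linear model on randomised arm adjusted for baseline motivation measured before the first mailing, provided the scale supports means. It is given with a 95% CI for each of the three contrasts, and no confirmatory claim is made. If baseline slopes clearly differ by arm, centred arm-by-baseline terms are included. Quit attempts and use of evidence-based treatment are described by arm, with between-arm differences and 95% CIs.*

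A bootstrap interval would suit the quit-attempt count if it is skewed. Separately, reconcile the two descriptions of the order of first survey and first mailing in Study Procedures and Interventions with the Consent Overview.

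The cost is a few sentences and one standard SPSS procedure. No new data are needed, because a baseline survey is already planned and the plan's own change in motivation requires a baseline score.
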